6.2 Schedule of Activities

Refer to the protocol (Section 1.3) for the complete Schedule of Activities.

6.3 Treatments

6.3.1 Treatments Administered

Study drug is defined as any investigational intervention(s), marketed product(s), or placebo intended to be administered to a participant according to the study protocol beginning on Cycle 1 Day 1.

Intervention Name	Tamibarotene	Tamibarotene-	Azacitidine
Type	Drug	Drug	Drug
Dose Formulation	Tablet	Tamibarotene- matched tablet	Reconstituted as solution or suspension
Unit Dose	2-mg tablets	Not applicable	100-mg single-use vials
Strength(s)			
Dosage Level and	6 mg BID; Days	3 tablets that	75 mg/m ² once per day;
D .	8 through 28 of	match	Days 1 through 7 of each
Regimen	each 28-day treatment cycle.	tamibarotene (BID); Days 8 through 28 of each 28-day treatment cycle	28-day treatment cycle. If dosing on Days 6 and 7 is not possible due to logistical limitations, these doses may be delayed to Days 8 and 9.
Route of Administration	Oral	Oral	Intravenous or subcutaneous
Use	Experimental	Placebo comparator	Background intervention

Table 2Study Treatments

Abbreviations: BID = twice per day

6.3.2 Method of Assigning Participants to Treatment Groups and Blinding

The study is double blinded, and randomization will be performed on Cycle 1 Day 1 using an interactive response system. Participants can be randomized earlier than Cycle 1 Day 1, but within 72 hours of the first dose of study drug, to accommodate operational needs.

Approximately participants with HR-MDS will be randomly assigned to study drug. Participants will be randomized 2:1 to receive either tamibarotene plus azacitidine or placebo plus azacitidine. Randomization will be stratified by the IPSS-R risk group (Intermediate, High, and Very High Risk). In addition, stratification of analyses by geographical region (North America, Western Europe, plus Israel, and Eastern Europe) will be performed, as there may be differences in available supportive care treatments and in access to subspecialty consultants and specialized hospital care among these regions. All participants, investigators, pharmacist(s) performing drug preparation, and site staff will be blinded to treatment assignment.

Personnel responsible for the bioanalysis of the tamibarotene concentrations in plasma will be provided with the randomization code in order to identify samples for analysis. The results will not be shared with the sponsor until the study is unblinded.

In addition, at the time of CR futility analysis, preliminary PK analysis will be performed by designated contract research organization (CRO), and the limited personnel from the CRO will have access to the unblinded PK data to build the population PK model.

To maintain study integrity, OS data will be kept blinded for Syros at the time of CR final analysis and beyond. Only 1 independent SAS programmer at Syros, who does not directly support this study, will have access to the OS data; the OS data will be stored in a separate study folder and can only be accessed by the independent SAS programmer. Further details will be outlined in the Blinding Maintenance Plan.

6.4 Efficacy and Safety Endpoints

Unless otherwise specified, all efficacy and safety endpoints will use participants' all available data up to the data cut-off.

6.4.1 Efficacy Endpoints

6.4.1.1 Primary Efficacy Endpoint and Estimand

The primary efficacy endpoint is CR defined as CR achieved by Cycle 7 Day 1, as determined by the investigator per the modified IWG MDS criteria (Cheson 2006). Peripheral blood counts to support the achievement of CR must be in the absence of transfusions or growth factors within the previous 7 days. The CR should be confirmed at least 4 weeks from the date of marrow sampling. Instructions for the assessment of IWG response including the provision of a 2-week window after the response assessment bone marrow aspiration for unscheduled hematology evaluations to meet the IWG criteria of CR are provided in the Study SY-1425-301 protocol, Section 8.1.1. The calculation of the rate of CR for each treatment group is:

CR rate (%) = number of *CR* responders achieved by Cycle 7 Day 1 / number of participants in the modified Intent-to-Treat (mITT) analysis set \times 100. The denominator is the mITT population in each treatment group.

Non-CR responders (mITT – CR responders) are participants who do not achieve CR or meet any of the following criteria:

Version 4.0

- 1. Do not have any post-baseline response assessments.
- 2. All response assessment results are missing or not done.
- 3. Discontinue prior to having a post-baseline assessment.
- 4. Withdraw consent before achieving a response.
- 5. Die before achieving a response.
- 6. Start a new anticancer therapy before achieving a response.
- 7. Experience prolonged treatment interruption requiring permanent withdrawal of study drug before achieving a response.

Table 3Primary Estimand

		Esti	mand Categ	ory	
		Population		Intercurrent	Populatio
		(Based on	Variable/	Event;	n Level
Objective	Treatment	mITT)	Endpoint	Strategy	Summary
CR: To demonstrate the superiority of tamibaroten e plus azacitidine compared to placebo plus azacitidine in CR in RARA- positive newly diagnosed HRMDS patients	Tamibaroten e plus azacitidine versus placebo plus azacitidine	RARA- positive participants with newly diagnosed HR-MDS according to the WHO classification , classified by the IPSS- R risk category as intermediate, high, or very high risk	CR achieved by Cycle 7 Day 1, as determined by the investigato r per the modified IWG MDS criteria (Cheson 2006)	Treatment discontinuation ; Treatment policy Participants who die, withdraw consent, or start a new anticancer therapy before achieving a response; Composite strategy	 CR rate by treatment arm Difference in proportion of CR rate between 2 treatment arms

Abbreviations: CR = complete remission; HR-MDS = higher-risk myelodysplastic syndrome; IPSS-R = Revised International Prognostic Scoring System; IWG = International Working Group; MDS = myelodysplastic syndrome; mITT = Modified Intent-to-Treat; RARA = retinoic acid receptor alpha; WHO = World Health Organization

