8.1.1 Response Assessment

Responses are evaluated per the modified IWG MDS criteria (Cheson 2006). A copy of the criteria is provided in Appendix 8. Note that resolution of dysplasia is not required for achievement of an IWG response. Physical examinations (Section 8.2.3) are scheduled at the time of all response assessments and include an assessment for the presence of extramedullary AML. Additional unscheduled hematology evaluations may be performed up to 2 weeks after the bone marrow aspiration, for those patients in marrow CR without full peripheral blood count recovery at the time of the bone marrow aspirate, to assess whether they meet IWG criteria for CR based on the results of this additional hematology evaluation. The CR date is assigned as the date of marrow sampling or peripheral count recovery, whichever is later.

In addition to on-treatment assessments, patients who have not progressed/relapsed will enter the Disease Follow-up period, during which response assessments will be performed every 3 months for response assessment until disease progression/relapse, death, or the occurrence of the expected number of OS events to support the final OS analysis, whichever occurs first. Response assessments during Disease Follow-up visits where the bone marrow aspirates are not performed, are based on hematology evaluation and physical examination findings.

Patients who progress/relapse will enter Survival Follow-up and will be followed to document the start of subsequent anticancer therapy, the date of disease progression/relapse, the date of transformation to AML, and OS status until the expected number of OS events to support the final OS analysis is observed.

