9.4.2 Primary Endpoint

Complete Remission

CR will be determined by the investigator per the modified IWG MDS criteria (Cheson 2006). Per the IWG MDS criteria responses must last at least 4 weeks. Instructions for the assessment of IWG response including the provision of a 2-week window for unscheduled hematology evaluations to meet the IWG criteria of CR are provided in Section 8.1.1.

The CR will be evaluated in the Intent-to-Treat (ITT) population. CR rate and 95% exact binomial confidence intervals (CIs) will be calculated by treatment group. Patients who do not have any post-baseline response assessment will be considered as non-responders and will be included in the denominator. The stratified Cochran–Mantel–Haenszel (CMH) test will be applied to compare the CR rates between the 2 treatment groups, stratified by IPSS-R risk group (Intermediate, High, and Very High Risk) and by geographical region (North America, Western Europe, and Israel versus Eastern Europe). The final analysis of CR is planned for the time when all 190 patients have completed the Cycle 7 Day 1 response assessment or discontinued treatment, whichever comes first. Patients with missing response assessment data will be considered as a failure to achieve CR, including patients who have died, withdrew consent, or started a new treatment prior to achieving a CR.

The point estimate of the difference of the proportions for CR rate between the 2 treatment groups will also be provided along with 95% CI.

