6.4.1.3 Secondary Efficacy Endpoints and Estimands

The secondary efficacy endpoints are:

• TI, defined as a period of at least 56 days with no red blood cell (RBC) or platelet transfusion since the date of randomization to the last dose of study drug + 30 days, the initiation of post-treatment therapy, or death, whichever occurs first. TI rate is calculated as:

TI rate (%) = number of participants who achieve TI / number of participants in the mITT analysis set \times 100. The denominator is the mITT population in each treatment group.

• Overall response, defined as achieving CR, partial remission (PR), marrow CR (mCR), or subcategories of hematologic improvement (HI), as determined by the investigator per the modified IWG MDS criteria (Cheson 2006). ORR will be calculated as:

ORR (%) = number of overall responders / number of participants in the mITT analysis set \times 100. The denominator is the mITT population in each treatment group.

Overall response may also be analyzed in line with the updated IWG response criteria (Zeidan 2023).

• DOCR, defined as the duration from the date of first documented evidence of CR to the date of documented relapse of disease or disease progression, as determined by the investigator per the modified IWG MDS criteria (Cheson 2006), or death due to any cause, whichever occurs first. Among CR responders, DOCR will be calculated in months as:

DOCR (months) = (first date of documented relapse of disease, disease progression, or death due to any cause - date of first documented evidence of <math>CR + 1) / 30.4375.

• Duration of overall response, defined as the duration from the date of first documented evidence of CR, PR, mCR, or HI, to the date of documented disease progression or relapse of disease, as determined by the investigator per the modified IWG MDS criteria (Cheson 2006), or death due to any cause, whichever occurs first. Among overall responders, duration of overall response will be calculated in months as:

Duration of overall response (months) = (first date of documented disease progression, relapse of disease, or death due to any cause - date of first documented evidence of CR, PR, mCR, or HI + 1) / 30.4375.

• Time to CR, defined as the duration from the date of randomization to the date of the first documented evidence of CR as determined by the investigator per the modified IWG MDS criteria (Cheson 2006). Among CR responders, this endpoint will be calculated as:

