Relapse after CR or PR						At least one of the following: Return to pretreatment BMB %. Decrement of ≥50% from maximum remission/response levels in granulocytes or platelets. Reduction in Hgb ≥1.5g/dL or transfusion dependence.
Cytogenet	Cytogenetic Response			1	1	1
Complete Partial			Disappearance of chromosomal abnormality with no appearance of new ones. ≥50% reduction of chromosomal abnormality			

Response Criteriaª		Peripheral Blood			BMB (%)	Other	
	Hemoglobin	Neutrophils	Platelets	Blasts			
	(g/dL)	per (L)	per (L)	(%)			
Disease Progression, participants with:		Evaluation C	Evaluation Criteria:				
<5% bone marrow blasts		\geq 50% increase to >5% bone marrow blasts					
5%-<10% l	bone marrow bla	sts	\geq 50% increase to >10% bone marrow blasts				
10%-<20%	0% -<20% bone marrow blasts \geq 50% increase t			e to ≥20%	bone marrow b	lasts	
For all categories			At least 50% decrease from maximum remission/response in granulocytes or platelets				
			or reduction in Hgb by ≥ 2 g/dL or transfusion dependence				

Abbreviations: BMB = bone marrow blasts; CR = complete remission; FAB = French-American-British; HI = hematologic improvement; Hgb = hemoglobin; IWG = International Working Group; mCR = marrow CR; MDS = myelodysplastic syndrome; PR = partial remission ^a Response must last at least 4 weeks.

The IWG criteria for HI define specific responses of cytopenias in the 3 hematopoietic lineages: erythroid (HI-E), platelet (HI-P), and neutrophil (HI-N). The HIs are measured in participants with pretreatment abnormal values: hemoglobin level less than 110 g/L (11 g/dL) or RBC-transfusion dependence, platelet count less than 100×10^9 /L or platelet-transfusion dependence, and absolute neutrophil count (ANC) less than 1.0×10^9 /L.

Table 8 Response Criteria for Hematologic Improvement for MDS

Hematologic Improvement	Response Criteria (Response Lasting 8 Weeks)
Erythroid response (pretreatment <11 g/dL)	Hgb increase by $\geq 1.5 \text{ g/dL}$
	Relevant reduction of units of RBC transfusions by an absolute
	number of at least 4 RBC transfusions/8 weeks compared with
	the pretreatment transfusion number in the previous 8 weeks.
	Only RBC transfusions given for a Hgb of $\leq 9.0 \text{ g/dL}$
	pretreatment will count in the RBC transfusion response
	evaluation.
Platelet response (pretreatment $<100 \times 10^{9}/L$)	Absolute increase of $\geq 30 \times 10^{9}$ /L if starting with $\geq 20 \times 10^{9}$ /L
	platelets

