7.4.3 Primary Efficacy Endpoint Analysis Methods

7.4.3.1 Primary Estimand Analysis for CR

The final analysis of CR is planned for the time when the first approximately **CCI** randomized participants out of the planned **CCI** participants have completed the Cycle 7 Day 1 response assessment or discontinued treatment, whichever comes first.

The primary endpoint is CR achieved by Cycle 7 Day 1, as determined by the investigator per the modified IWG MDS criteria (Cheson 2006). There is expected to be a high correlation between CR achieved by Cycle 7 Day 1 and CR achieved at any time (Silverman 2006; VIDAZA UPSI), and therefore, the same effect size and other design assumptions are justified in the hypothesis testing below. The objective is to demonstrate the superiority of tamibarotene plus azacitidine compared to placebo plus azacitidine in CR in RARA-positive newly diagnosed HR-MDS participants.

The null hypothesis (H₀) to be tested is:

In RARA-positive participants with newly diagnosed HR-MDS, CR rate for participants in the tamibarotene plus azacitidine treatment group is the same as the CR rate for participants in the placebo plus azacitidine treatment group.

The alternate hypothesis (H_A) to be tested is:

In RARA-positive participants with newly diagnosed HR-MDS, CR rate for participants in the tamibarotene plus azacitidine treatment group is higher than the CR rate for participants in the placebo plus azacitidine treatment group.

The following analyses will be conducted separately:

- [1] Primary analysis of primary estimand (investigator response in mITT analysis set)
- [2] Sensitivity analysis of primary estimand (investigator response in ITT analysis set)
- [3] Sensitivity analysis of primary estimand (investigator response in PP analysis set)

The CR rate and 95% exact binomial CIs based on the Clopper-Pearson exact method will be calculated by treatment group.

Confidential

Syros Pharmaceuticals, Inc. SY-1425-301

The CR rate will be analyzed using the Cochran-Mantel-Haenszel (CMH) test to compare the 2 treatment groups with a 1-sided 2.5% level of significance. The strata for the test will be those used for stratified randomization, with potential pooling of strata if there is insufficient information in any stratum; the pooling strategy is specified in Section 7.4.2. The point estimate of the difference of the proportions for CR rate between the 2 treatment groups will be provided along with its 95% CI.

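### SAP 6.4.1.1 counts the 4-week CR confirmation from the marrow date, but the protocol can date the CR up to 14 days later, so confirmation can come before the response has lasted 4 weeks

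*SAP*

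**What the plan says.** SAP 6.4.1.1 sets the confirmation rule for the primary endpoint: "The CR should be confirmed at least 4 weeks from the date of marrow sampling". Its next sentence adopts, by reference to protocol 8.1.1, "the provision of a 2-week window after the response assessment bone marrow aspiration for unscheduled hematology evaluations to meet the IWG criteria of CR".

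Protocol 8.1.1 describes that window for patients in marrow CR without full count recovery: "Additional unscheduled hematology evaluations may be performed up to 2 weeks after the bone marrow aspiration". It then fixes the start of the remission: "The CR date is assigned as the date of marrow sampling or peripheral count recovery, whichever is later".

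On duration, protocol 9.4.2 states "Per the IWG MDS criteria responses must last at least 4 weeks". The footnotes to protocol Appendix 8 and SAP Table 7 say the same; in the SAP, "Response must last at least 4 weeks".

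On the deadline, SAP 7.4.3.1 states: "The primary endpoint is CR achieved by Cycle 7 Day 1, as determined by the investigator".

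Neither document says which date governs confirmation when count recovery follows the marrow. The change summaries in SAP section 8 do not mention the marrow anchor. The full list of Version 2.0 changes is in a separate document that was not available.

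**The concern.** The confirmation clock and the remission can start on different days. For a patient whose marrow qualifies but whose counts recover later, the SAP starts the 4 weeks at the marrow, while the protocol starts the CR at recovery. Confirmation can then be reached before the response has lasted the 4 weeks that both documents require. Responder status in the primary analysis is at stake, and OS is tested only if CR is significant (SAP 7.1.1).

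The same window creates a secondary ambiguity at the deadline. If the Cycle 7 Day 1 marrow qualifies and counts recover some days later, protocol 8.1.1 dates the CR after Cycle 7 Day 1. The SAP grants the window but does not say whether such a patient has achieved CR in time.

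**Working it through.** This is date arithmetic. It does not depend on sample size, power or alpha, and the plan states no figure to reproduce.

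**Inputs**
- Confirmation: at least 28 days after the marrow (SAP 6.4.1.1).
- Lag from marrow to count recovery, r: 0 to 14 days (protocol 8.1.1, adopted in SAP 6.4.1.1).
- CR date: the later of marrow and recovery (protocol 8.1.1).
- Required duration: at least 28 days (protocol 9.4.2 and Appendix 8; SAP Table 7).
- From Cycle 2, scheduled hematology on Day 1 of each 28-day cycle, ±3 days (protocol 1.3).

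**Formulas**, with the marrow on day 0
- CR date = max(0, r) = r.
- Age of the CR at the earliest SAP confirmation = 28 - r.
- Earliest day on which the CR is 28 days old = 28 + r.

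| r (days) | CR age on day 28 | Day the CR reaches 28 days | First undelayed Day 1 count on or after that day |
|---|---|---|---|
| 0 | 28 | 28 | 28 |
| 3 | 25 | 31 | 56 |
| 7 | 21 | 35 | 56 |
| 10 | 18 | 38 | 56 |
| 14 | 14 | 42 | 56 |

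At r = 0 the two rules agree, so the shortfall appears only with late recovery. The inclusive duration convention in SAP 7.1.4 adds one day, which makes the worst case 15.

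**Can it happen on the ordinary schedule?** Yes. In an undelayed cycle the next Day 1 count falls on day 28. Over days 28 to 31, the late side of the visit window, a CR with r = 14 is 14 to 17 days old.

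**When does status change?** Only when CR is confirmed between day 28 and day 28 + r and is lost before day 28 + r. For example, counts recover on day 14, hold on day 28 and meet relapse criteria on day 35. The confirmation sentence is met, but the CR lasted 35 - 14 = 21 days and fails Table 7.

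**Deadline.** With a qualifying Cycle 7 Day 1 marrow and recovery on day 10, the protocol CR date is 10 days after Cycle 7 Day 1.

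**The case against.** The strongest reply is that the SAP never waives the duration criterion. The endpoint is defined by the modified IWG criteria, and Table 7 applies those with its 4-week footnote. The confirmation sentence sets a minimum interval, so both conditions can be applied together, and a 14-day CR would then be rejected. This stands in part. A reader might infer that the SAP plainly accepts 14-day remissions, and the documents do not support that. They do contain an explicit confirmation rule that such a remission satisfies and a footnote that it fails, with nothing to rank them.

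Second, the SAP does not say what evidence confirms a CR. Scheduled response assessments fall on Day 1 of Cycles 2 and 4 and then every third cycle, so the next one comes 56 or 84 days after the marrow. With r = 14 the CR would then be 56 - 14 = 42 or 84 - 14 = 70 days old, and the requirement is met. This stands as a condition on the finding: the shortfall needs an interim count or an extra assessment. Nothing rules that out, and the plan elsewhere bases some response assessments on hematology and physical examination without a marrow (protocol 1.3, note y).

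Third, the natural reading of the deadline is that the Cycle 7 Day 1 assessment includes its 2-week window, because the same SAP section grants both. That is fair. A reader might infer that these responders are lost from the primary analysis, but the text only leaves the matter unstated.

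Fourth, the investigator who determines response is blinded and the rule is the same in both arms. No bias between arms and no type I error effect has been shown.

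**Conclusion.** The confirmation sentence in SAP 6.4.1.1 conflicts with the CR date in protocol 8.1.1 and with the 4-week duration in protocol 9.4.2, Appendix 8 and the SAP's own Table 7. The CR can be as little as 28 - 14 = 14 days old when the sentence is met. This applies only to patients whose counts recover after the marrow, and only if confirmation falls between day 28 and day 28 + r.

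The effect on the CR rate or the treatment difference cannot be computed. The assumed CR rates are redacted, and the documents do not give the share of CRs reached by late recovery or the share lost before day 28 + r. A reader might set single patients against the final boundary of 0.1349. With the 190 patients of protocol 9.4.2 split 2:1 (about 127:63), one patient moves the difference by 1/127 = 0.8 or 1/63 = 1.6 percentage points. That is the weight of one patient and says nothing about how many would be reclassified.

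A reader might also infer that DOCR and time to CR are misdated. They are not: in the SAP, "DOCR, defined as the duration from the date of first documented evidence of CR", and time to CR ends on that same date. They are affected only through who is included.

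This is a real inconsistency in a primary-endpoint rule. It should be settled before unblinding, but it is not shown to threaten the primary result.

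**What to change.** In SAP 6.4.1.1, replace the confirmation sentence with: CR must still be present at least 28 days after the CR date, which is the later of marrow sampling and peripheral count recovery (protocol 8.1.1).

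Add: a CR whose qualifying marrow was taken at or before the Cycle 7 Day 1 assessment counts as achieved by Cycle 7 Day 1 if counts recover within the 14-day window.

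If the sponsor intends the marrow date to govern, the SAP should say so and reconcile this with protocol 8.1.1, 9.4.2, Appendix 8 and Table 7. A sensitivity analysis should then count only CRs lasting at least 28 days from the CR date.

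The text change is two sentences, but there is a cost in data. The CR rate may be slightly lower. Recovery on day 14 needs an unscheduled count on day 42 or later, or the Day 1 count at about day 56. For a Cycle 7 Day 1 marrow that is about Cycle 9 Day 1, whereas the CR analysis is triggered by completion of the Cycle 7 Day 1 assessment or discontinuation of treatment. The present rule already needs 28 days after that marrow. The new one needs up to 42 - 28 = 14 days more with an extra count, or 56 - 28 = 28 days more on scheduled counts. The CR data cut-off should be set to allow for this.

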- (aa) Response assessment bone marrow aspirates will be collected on Day 1 of Cycles 2 and 4, followed by every third cycle (7, 10, 13, etc.), and at EoT, with bone marrow aspirates collected at other times as clinically determined. Following the C7D1 response assessment, those in CR may have the frequency of bone marrow aspirates for response assessment reduced to every 6 cycles. The samples for the local assessment of response (blast count and cytogenetics) are required. In addition, an aspirate smear will be collected and sent to the Central Laboratory for central review. At C4D1, C7D1, every 6 cycles thereafter, as well as at EoT, an additional aspirate sample will be collected and sent to the Central Laboratory for exploratory analyses (Section 8.6.3). A bone marrow biopsy may be performed at investigator's discretion to supplement the interpretation of the bone marrow aspirate.
- (bb) Response assessment bone marrow aspirates will be collected every 3 months during the Disease Follow-up period, with bone marrow aspirates collected at other times as clinically determined. Patients in CR may have the frequency of bone marrow aspirates for response assessment reduced to every 6 months. The samples for the local assessment of response (**blast count** and **cytogenetics**) are required. In addition, an aspirate smear for **central review** will be collected and sent to the Central Laboratory. An additional aspirate sample should be collected if possible and sent to the Central Laboratory for exploratory analyses (Section 8.6.3). A bone marrow biopsy may be performed at investigator's discretion to supplement the interpretation of the bone marrow aspirate.
- (cc) The morning dose of tamibarotene/placebo will be taken in the clinic on C1D8, C1D22, and D15 of Cycles 2 through 4; date/time of dose should be recorded.
- (dd) If dosing on Days 6 and 7 of a cycle is not possible due to logistical limitations, these doses may be delayed to Days 8 and 9. Tamibarotene/placebo is permitted to overlap with azacitidine on Days 8 through 9 of this alternative schedule. If criteria for azacitidine dose hold are met (Table 1), tamibarotene/placebo dosing may continue, unless criteria for tamibarotene/placebo hold are also met. D1 of the next treatment cycle is delayed until azacitidine dosing may resume.
- (ee) Peripheral blood samples will be sent to the Almac Diagnostics Laboratory for assessment of RARA biomarker to determine study eligibility.

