An EoT Visit should occur within 3 days of the last dose of study drug (or within 3 days of decision to permanently stop drug treatment, if this decision directly follows a period when drug has been on hold) and before the start of any subsequent anticancer therapy. A Safety Follow-up Visit should occur 30 days (± 3 days) after the EoT Visit and if possible before the start of any subsequent anticancer therapy. After the EoT Visit, patients who have not progressed/relapsed will enter the Disease Follow-up period, during which response assessments will be performed for up to 5 years after discontinuation of study drug (irrespective of initiation of HSCT or other subsequent anticancer therapy) or until disease progression/relapse, death, or the occurrence of the expected number of OS events to support the final OS analysis, whichever occurs first. It is estimated that a final analysis of OS will occur approximately 70 months following the enrollment of the first patient.

Patients who progress/relapse will enter Survival Follow-up and will be followed to document the start of subsequent anticancer therapy, the date of disease progression/relapse, the date of transformation to AML, and OS status until the expected number of OS events to support the final OS analysis is observed.

An IDMC will be established and will review the data at the 2 planned interim futility analyses and the safety interims, as specified in the IDMC Charter.

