9.4.3 Key Secondary Endpoint

Overall Survival

OS, defined as the time from the date of randomization to the date of death due to any cause, will be analyzed in the ITT population. Patients who do not die at the time of a data cutoff date

(interim and/or final) will be censored at the last date the patient is known to be alive or at the analysis cutoff date, whichever is earlier.

The distribution of OS will be estimated for each treatment group using Kaplan-Meier methodology and compared between 2 treatment groups using the log-rank test stratified by IPSS-R risk group (Intermediate, High, and Very High Risk) and by geographical region (North America, Western Europe, and Israel versus Eastern Europe). The hazard ratio and the corresponding 95% CI between the 2 treatment groups will be estimated using the stratified Cox proportional hazards model with the same stratification factors that are used for stratified log-rank test. OS will be displayed by Kaplan-Meier curves. The 25th percentile, median, and 75th percentile OS and the 95% CI will be provided for each treatment group. The 12-month and 24-month OS rates will be estimated using the Kaplan-Meier method.

Table 3: Estimands (Primary and Key Secondary)

	Estimand Category					
Objectives	Treatment	Population	Variable/Endpoint	Intercurrent Event; Strategy	Population Level Summary	
CR: To demonstrate the superiority of tamibarotene plus azacitidine compared to placebo plus azacitidine in CR in RARA-positive newly diagnosed HR-MDS patients	Tamibarotene plus azacitidine versus placebo plus azacitidine	RARA-positive patients with newly diagnosed HR-MDS according to the WHO classification, classified by the IPSS-R risk category as intermediate, high, or very high risk	CR, as determined by the investigator per the modified IWG MDS criteria (Cheson 2006)	Treatment discontinuation; Treatment policy Patients who die, withdraw consent, or start a new anticancer treatment before achieving a response; Composite strategy	 CR rate by treatment arm Difference in proportion of CR rate between two treatment arms 	

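### SAP 6.4.1.1 item 7 scores one form of treatment discontinuation as non-CR, although both estimand tables handle discontinuation by treatment policy

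*SAP*

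**What the plan says.** SAP 6.4.1.1 defines the primary endpoint as CR by Cycle 7 Day 1, judged by the investigator. It adds a confirmation rule: "The CR should be confirmed at least 4 weeks from the date of marrow sampling". It then says that non-CR responders "are participants who do not achieve CR or meet any of the following criteria", followed by seven items. Items 1 and 2 concern absent or missing assessments. Item 3 concerns discontinuation before any post-baseline assessment. Items 4 to 6 are consent withdrawal, death and new anticancer therapy before a response. Item 7 is "Experience prolonged treatment interruption requiring permanent withdrawal of study drug before achieving a response".

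The estimand in the same SAP section (Table 3) gives "Treatment discontinuation ; Treatment policy". Protocol Table 3 gives the same for CR: "Treatment discontinuation; Treatment policy". In both tables the composite strategy covers only death, consent withdrawal and new anticancer therapy. Protocol 9.4.2 treats missing response data as failure, "including patients who have died, withdrew consent, or started a new treatment prior to achieving a CR". It names neither interruption nor withdrawal of study drug.

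**The concern.** Permanent withdrawal of study drug is treatment discontinuation. Under treatment policy, a CR observed after discontinuation counts. Under item 7 it does not, if the discontinuation followed a prolonged interruption and came before a response. Two programmers, one working from the list and one from Table 3, would code the same participant differently.

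This is the only primary endpoint, and under SAP 7.1.1 overall survival is tested only if it succeeds. A recoded CR would also drop out of duration of CR and time to CR, because both are restricted to participants with CR by Cycle 7 Day 1. None of the CR sensitivity or supplementary analyses in SAP 7.4.3 varies item 7. If the conflict is noticed only after unblinding, settling it becomes a post hoc choice.

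**Working it through.** **1. The rules side by side**

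| Event before a response | SAP 6.4.1.1 list | SAP Table 3 | Protocol Table 3 | Protocol 9.4.2 |
|---|---|---|---|---|
| Death | failure (item 5) | composite | composite | failure |
| Consent withdrawal | failure (item 4) | composite | composite | failure |
| New anticancer therapy | failure (item 6) | composite | composite | failure |
| Permanent withdrawal after prolonged interruption | failure (item 7) | treatment policy | treatment policy | not listed |

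Item 7 is the row that disagrees. Item 3 also rests on discontinuation. Read literally, it could reach someone who stops early and has the first marrow at End of Treatment (EoT).

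**2. Can the conflicting case occur?**

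Yes. Protocol 4.1 places EoT after a hold "within 3 days of decision to permanently stop drug treatment, if this decision directly follows a period when drug has been on hold", and before any subsequent anticancer therapy. The Schedule of Activities (footnote aa) collects response marrows "followed by every third cycle (7, 10, 13, etc.), and at EoT". Under protocol 8.1.1, blood counts may recover up to 2 weeks after the marrow, and the CR date is the later of the two. A first CR can therefore be dated after the decision to stop permanently.

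Later visits add little:
- Nominal Cycle 7 Day 1 with no delays (an assumption) is 6 × 28 + 1 = Day 169.
- Taking 3 months as 91 days, the first Disease Follow-up visit falls by Day 169 only if EoT is by Day 169 − 91 = 78. At the −14-day edge of the window this becomes Day 169 − 77 = 92.

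The EoT marrow is therefore the main route.

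**3. Confirmation at 4 weeks**

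Safety Follow-up falls 30 ± 3 days after EoT, that is 27 to 33 days, against the 28 days needed. Protocol 7.1 allows that visit to be combined with EoT when EoT is at least 30 days after the last dose. The interruption criterion in 7.1 is at least 28 days, and EoT may come up to 3 days after the decision to stop: 28 + 3 = 31. A combined visit is therefore likely in this group. The next scheduled hematology is then Disease Follow-up at 3 months, for participants who have not progressed or relapsed.

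**4. Size of one reclassified CR**

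- Plan's figure: SAP 7.4.7.1 sets the CR futility look at the 95th participant and information fraction 0.5, so N = 95 / 0.5 = 190. This agrees with the 190 in protocol 9.4.2. It cannot be rebuilt from power, because power and CR rates are redacted.
- The mITT size is redacted in the SAP, so 190 is an assumption here. Split 2:1, it gives about 127 and 63.
- Active arm: 100 / 127 = 0.79 points, lowering the difference. Control arm: 100 / 63 = 1.59 points, raising it.
- One in each arm: 1.587 − 0.787 = +0.80 points. Two active and one control: 1.587 − 1.575 = +0.01 points.
- For N = 180 (120 and 60): 0.83 and 1.67 points. For N = 200 (133 and 67): 0.75 and 1.49 points.
- For scale, the final critical difference in SAP Table 16 is 13.49 points. The steps for N = 190 are 0.787 / 13.49 = 5.8% and 1.587 / 13.49 = 11.8% of it.

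These steps describe any single reclassified CR under any rule. They say nothing about how many item 7 would reclassify.

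**The case against.** The best defence is that the list merely describes participants without CR, since the SAP labels the group as mITT minus CR responders. That does not hold. Item 6 must be able to override an observed CR, because a CR after new therapy is a composite failure. The list is a derivation rule joined by *or*, and item 7 works in the same way.

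The argument from narrowness does stand. The case needs no earlier response, a prolonged hold, a permanent stop, then a CR with no new therapy. Counts must be free of transfusion and growth factors for 7 days, and confirmation must follow at 4 weeks. If *response* in item 7 means any IWG response, earlier hematologic improvement or marrow CR removes more people. The count could be zero.

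Four stronger readings are tempting but unsupported:

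- **Item 7 catches anyone who stops a single component.** Protocol 6.5.1 does let one drug stop while the other continues, and the note to protocol Table 1 concerns tamibarotene alone. But protocol 7.1 refers to interruption of both drugs, and the SAP does not settle the point. The wider reach is possible, not established.
- **The SAP's visit-label rule excludes off-treatment assessments from the CR derivation.** SAP 7.1.2 governs by-visit summaries, not this derivation.
- **Item 7 is an undeclared change from the protocol.** SAP Section 8.3 refers to a separate full list of Version 2.0 changes that is not available here, so this cannot be judged.
- **Item 7 biases the result or costs power in a known way.** The documents give no withdrawal rates by arm and no later CR rates.

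**Conclusion.** The inconsistency is real: the primary endpoint's derivation contradicts its estimand in both documents. It affects only permanent withdrawals that follow a prolonged interruption and precede a response. Withdrawals for other reasons, and CRs reached before withdrawal, are not touched by item 7. The affected group is mainly participants with a first CR at the EoT marrow, or by count recovery within 2 weeks of it. It would be larger only if stopping one component is enough. The number affected and the direction are unknown. The step sizes of 0.79 and 1.59 points rest on the assumed 127 and 63. Confidence is high on the textual conflict only; a material effect on the result is not shown. The point is worth correcting because it concerns the sole primary endpoint and is cheap to settle before unblinding.

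**What to change.** Before unblinding:

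1. Delete item 7 from the primary CR derivation.
2. Limit item 3 to participants with no post-baseline response assessment at all. Items 1 and 2 already cover them, so discontinuation alone would never override an observed CR.
3. State that a CR by Cycle 7 Day 1 counts if it meets the SAP's existing 4-week confirmation rule and precedes death, consent withdrawal and new anticancer therapy, using assessments already scheduled.
4. Report the item 7 version as a sensitivity analysis, saying whether one or both components must stop and whether *response* means CR.

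The cost is one SAP edit and one extra table, with no new visits. The limitation is that some off-treatment CRs may stay unconfirmed, because Safety Follow-up may be merged with EoT and the next scheduled hematology is then 3 months later.
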